Study Duration	For each patient the time periods are as follows: Screening: 28 days or longer based on local practice standard of care Treatment period: 84 days Observation post treatment period: 84 days
Study Center(s)	Multi-center clinical trial with approximately 20-40 sites
Objectives	To compare the effectiveness, safety (tolerability), and duration of treatment response at 12 weeks of home versus office-based narrowband ultraviolet B phototherapy for the treatment of psoriasis
Number of Subjects	1050 Stratified by Fitzpatrick skin type (350 skin type I/II, 350 skin type III/IV, 350 Skin type V/VI)

	 Inclusion criteria: Willing and able to provide informed consent (age 18+) or parental permission and assent (ages 12-17) Age 12 or older Plaque or guttate psoriasis predominantly located on trunk and/or extremities, with a physician global assessment average of >1.0, and considered a candidate for phototherapy Patient is deemed willing and able to comply with either in-office or inhome phototherapy: In office: Able to travel about 3 times per week for 12 weeks from home, work and/or school during business hours of local site In home: Has space to accommodate home phototherapy
	home phototherapy instructions 5. New or established patient in the practice
Main Inclusion and Exclusion Criteria	 Exclusion criteria: Patients who are judged unable or unwilling to comply with either in office or in home phototherapy due to time, work, school, or other financial constraints Patients judged unable to follow home phototherapy protocol due to failure to demonstrate understanding of the following: a. How to operate the phototherapy device b. How to follow the dosing protocol c. Requirement to wear protective eyewear and genital protection equipment Patients with known history of lack of efficacy to phototherapy or treated with phototherapy 14 days prior to baseline visit Psoriasis predominantly located on scalp, body folds, genitals, palms and/or soles or with a physician global assessment average of ≤ 1.0 Patients deemed unsafe to be treated with phototherapy: a. History of photosensitivity or autoimmune disease such as lupus or dermatomyositis which can be aggravated by ultraviolet radiation b. History of melanoma or multiple non-melanoma skin cancers that in the opinion of the principal investigator contraindicates treatment with phototherapy
Comparator Device	Daavlin 7 series 3 panel narrow band phototherapy home units (have 8-12 bulbs and a smaller, flat surface with door, measuring 21" wide, 74.5" tall, and 23.5"). The unit will have a dosimetery controller, a UV sensor built in that measures the intensity of the light. This unit is a class II device with a FDA 510K indication for psoriasis, vitiligo and atopic dermatitis/eczema.
Duration of administration (if applicable)	Approximately three times per week x 12 weeks

Reference therapy	Office based narrow band phototherapy (units typically have at least 24 bulbs in a surround structure)
Statistical Methodology	 The co-primary endpoints of this study will be: Physician Global Assessment (PGA) score of clear/almost clear (at week 12 or the time of phototherapy discontinuation, whichever comes first) Dermatology Life Quality Index (DLQI) score of ≤5 which corresponds to no to small impact of dermatologic disease on quality of life at week 12 Secondary outcomes include: Physician measured body surface area (BSA) x PGA Concomitant topical psoriasis treatment Patient reported time spent on phototherapy Patient reported time and cost associated with travel for phototherapy treatments Phototherapy number and dose Duration of treatment response during observation period
Safety Evaluations	The primary safety outcome is the proportion of patients reporting treatment- emergent adverse events. Treatment emergent adverse events include patient reported burns and their severity. We will also collect data on all Serious Adverse Events whether treatment related or not.
Data and Safety Monitoring Plan	The local investigators are responsible for monitoring patient safety as per standard of care. Data quality will be monitored by the study Principal Investigator and his team centrally with queries and auditing of sites as necessary.

BACKGROUND AND STUDY RATIONALE

This study will be conducted in full accordance all applicable University of Pennsylvania Research Policies and Procedures and all applicable Federal and state laws and regulations including 45 CFR 46, 21 CFR Parts 50, 54, 56, and Good Clinical Practice: Consolidated Guidelines approved by the International Conference on Harmonisation (ICH).

Narrow band ultraviolet B (NB-UVB) phototherapy is a first line standard of care treatment for psoriasis. While being highly preferred by providers and patients its use is limited by inconvenience as patients must travel to the provider's office about 3 times per week for 12 weeks. Home phototherapy is an accepted alternative but relatively limited data in the U.S. has led to decisional uncertainty and thus wide variation in insurance coverage and utilization by physicians. We will therefore conduct a large pragmatic trial of home vs. office based phototherapy for the treatment of psoriasis. A pragmatic trial aims to reflect real world clinical practice as closely as possible and therefore provides the best estimates of effectiveness, or generalizability of the results to the intended treatment population¹. We hypothesize that NB-UVB phototherapy treatment of moderate to severe psoriasis at home will be non-inferior to office treatment according to outcomes that matter to patients, providers, and payers. It is possible that home vs. office based phototherapy will be associated with differences in tolerability (i.e., burns) in those with very fair skin type (i.e., type I/II) due to increased penetration of ultraviolet rays, and may be associated with differences in effectiveness in darker skin types (type V/VI) due to decreased penetration of ultraviolet rays. Therefore, the study will be stratified by skin type to test for non-inferiority in specific patient sub groups.

1.1 Background and Relevant Literature

Psoriasis is a common chronic inflammatory disease that affects over 8 million Americans². The annual U.S. cost of psoriasis amounted to approximately \$112 billion in 2013³. The onset of psoriasis most commonly occurs in young adulthood but may start at any age ranging from the perinatal period to patients in their nineties⁴. Psoriasis affects all races and ethnicities. It is slightly more common in Caucasians compared to African Americans; however, African Americans are reported to have more severe disease⁵. Once psoriasis starts, it is a chronic, incurable, life-long disease, with durable spontaneous remissions being rare. Psoriasis is characterized by thick, inflamed, red patches (called plaques), with silver adherent scale. Plaques may be painful, itch, or burn and frequently bleed resulting in stains to clothes and bedding. Any area of the body can be affected including the face, trunk, extremities, palms, soles, genitals, and nails. Psoriasis is not "just a skin disease". It has profound impacts on health related quality of life that are similar to or more significant than other major disorders such as cancer, cardiovascular disease, and depression^{6, 7}. Indeed, patients with psoriasis, particularly when disease is more extensive, have an increased risk of diabetes, chronic kidney disease, and major cardiovascular events independent of traditional risk factors, culminating in an estimated 5-year reduction in life expectancy⁸⁻¹².

The cause of psoriasis is unknown. There is genetic susceptibility with 40% of patients having a positive family history¹³. Over 80 genes predisposing to psoriasis have been identified with HLA-C gene Cw6 serotype being most commonly implicated¹³. Psoriasis is a prototypical example of a Th1/Th17 inflammatory disease characterized by increased activity of lymphocytes, antigen presenting cells, monocytes, and neutrophils resulting in dramatic increases in epidermal hyper proliferation and angiogenesis¹⁴. For example, in normal skin it takes 30 days for keratinocytes (the primary cell of the epidermis) to turn over, whereas this process takes only 2-3 days in a patient with psoriasis.

Treatment of psoriasis includes topical ointments, ultraviolet light phototherapy, oral medications such as methotrexate, and injectable biologics¹⁵. Treatment selection is based on objective factors (extensiveness of disease and anatomic areas involved) and subjective factors such as symptoms and impacts on health related quality of life. When disease is more extensive, typically affecting 3-10% (moderate) or >10% (severe) of the body surface area, topical medications are unable to control the disease and thus systemic medications or phototherapy is indicated¹⁵. It is estimated that about 20% of patients with

psoriasis have moderate to severe disease, culminating in over 1.5 million people in the United States². Despite advances in treatments, psoriasis, particularly when moderate to severe, remains widely untreated and patients remain dissatisfied with their level of disease control¹⁶. For example, it is estimated that 70-90% of patients with severe psoriasis are currently not receiving systemic or phototherapy^{17, 18}. Thus, the overwhelming majority of patients with moderate to severe psoriasis in the US live for decades with their disease poorly controlled¹⁹. Moreover, disparities exist in that African Americans are more likely to experience moderate to severe psoriasis compared to whites yet are 70% less likely to receive treatments for moderate to severe psoriasis^{5, 20}.

Phototherapy is a preferred first line treatment because oral medications can result in serious organ damage and/or significant gastrointestinal intolerance and biologics suppress the immune system and have warnings for infections and malignancy²¹²². Phototherapy was first used to treat psoriasis in the 1920s and is a widely accepted standard of care²³. In the 1980's split body studies demonstrated that NB-UVB (311 nm) was more efficacious than traditional broadband (290-320 nm) ultraviolet B (UVB) phototherapy²³. It is important to distinguish narrowband phototherapy, which can be delivered via medical devices in the home or office, from commercial tanning beds which deliver predominantly ultraviolet A radiation and are ineffective for psoriasis. Guidelines of care issued by the American Academy of Dermatology highlight that NB-UVB phototherapy is a widely accepted, first line, standard of care treatment and also indicate that patients with psoriasis who are compliant, motivated, and adherent with instructions and follow-up examinations could, under dermatologist supervision, be considered appropriate candidates for home NB-UVB therapy²³. Phototherapy remains a critical therapeutic modality that is much more widely prescribed by dermatologists than systemic treatments such as biologics (which are prescribed only by an estimated 20% of dermatologists)²⁴. Although phototherapy does not treat psoriatic arthritis (PsA), it is often used to augment response to systemic agents and the majority of patients do not have PsA^{23, 25}. Despite home phototherapy being highly preferred by patients, as summarized by a recent review of psoriasis treatment for UptoDate, "uncertainty regarding the safety of home units has led to a reluctance to prescribe them."²⁶ NB-UVB requires treatments three times per week for 12 weeks in order to achieve optimal skin clearance. Treatment may then continue on a maintenance basis (1-2 times per week) or be stopped and then restarted when psoriasis recurs and is symptomatic enough that the patient desires another course of phototherapy²⁷. As a result, office based phototherapy is highly burdensome for patients who need to take time off from work and family to receive treatment. Moreover, only about 10% of counties in the US offer office based phototherapy²⁸.

1.2 Name and Description of the Comparator Product

Daavlin 7 series 3 panel narrow band phototherapy home units have 8-12 bulbs and a smaller, flat surface with a door, and measure 21" wide, 74.5" tall, and 23.5". The unit will have a dosimetry controller, a UV sensor built in that measures the intensity of the light. This unit is a class II device with an FDA 510K indication for psoriasis, vitiligo and atopic dermatitis/eczema.

1.2.1 Nonclinical Data

Not applicable

1.2.2 Clinical Data to Date

Both home and office based phototherapy are widely accepted as standard of care for patients with psoriasis as evidenced by American Academy of Dermatology treatment guidelines²³. A recent systematic review identified nine randomized controlled trials of office-based NB-UVB phototherapy involving a total of 293 patients. The average response rate based on a 75% improvement in the Psoriasis Area and Severity Index (PASI 75) was 65% (95% CI 45-79) (PASI 75 is similar clinically to being clear/almost clear by PGA)²⁹. Home phototherapy was introduced in the 1970's; however, rigorous published studies are scant. There is only one controlled trial of home narrowband phototherapy versus office-based phototherapy (no other randomized controlled studies exist)³⁰. The study was conducted in the Netherlands at 14 Dermatology Departments located in hospitals with the majority of patients coming from just 4 centers. 94 patients were treated at home and 91 in the office. 41% of patients achieved a PASI75 in both groups and the authors concluded that UVB phototherapy administered at home is

equally safe and equally effective, both clinically and for quality of life, as UVB phototherapy administered in an outpatient setting³⁰.

1.2.3 Clinical Studies in Children

Phototherapy is generally effective and safe in children and is considered standard of care for the treatment of pediatric psoriasis;³¹⁻³⁴ however, prospective trials are very limited. To date, there have been 2 prospective studies of office-based UVB therapy in pediatric patients with psoriasis. Twenty children between the ages of 6 and 14 years old were enrolled in a single-center trial of twice weekly NB-UVB in a dermatology clinic in India, with 12 (60%) showing PASI 90, 3 (15%) showing PASI 70-90, 1 (5%) showing PASI 50-70, and 2 (10%) showing less than PASI 50 or worsening disease after 12 weeks³⁵. The only reported adverse event was mild erythema in 2 (10%) patients. The same center also performed a prospective single-blinded trial comparing twice weekly NB-UVB versus NB-UVB with mineral oil pretreatment in a split-body design; of the 18 patients analyzed, both groups had large reductions in the mean modified PASI score (mean baseline score of 15.3 to scores of 0.64 and 0.14 at 12 weeks in the NB-UVB and NB-UVB mineral oil pretreated groups, respectively)³⁶.

The majority of efficacy and safety data for UVB use in pediatric psoriasis in the literature are based on retrospective reviews. In one of the largest reviews to date, 79 children with psoriasis were treated with NB-UVB at a single institution in Israel between 1998-2006; among them, 40 (51%) achieved complete clearance, 33 (41%) at least 75% improvement, and 6 (8%) less than 75% improvement. Side effects were minor and included 13 (15%) patients with mild erythema, 2 (1%) with itch, and 3 (3%) with burning³⁷. In other smaller retrospective reviews, response rates have ranged from 63-88% of patients achieving clear or almost clear skin; 45-86% of patients achieving 90% improvement in PASI or BSA; 17-40% of patients achieving 70-90% improvement in PASI or BSA; 20-22% of patients achieving 50-70% improvement in PASI; and 9-15% of patients with minimal or no improvement³⁸⁻⁴³. There have been no published studies of home UVB phototherapy for pediatric psoriasis; however, home phototherapy is widely accepted by US dermatologists for the treatment of children with psoriasis and other light responsive disorders.

1.3 Dose Rationale

The initial dose of NB-UVB phototherapy is based on skin type. The dose is then gradually increased as tolerated based on an easy to follow algorithm (see Appendix A for examples). The initial treatment may only require 20 seconds of phototherapy exposure, which then may range to up to approximately 5-10 minutes of exposure time. The ideal dose causes mild transient pinkness of the skin that lasts < 24 hours. There are six skin types which are grouped into 3 sub-groups based on the anticipated minimal erythema dose response to phototherapy: Type I and II (white; very fair; red or blond hair; blue or green eyes; freckles, usually or always burns, never tans or tans with difficulty), Type III and IV (cream white to olive brown skin, sometimes to rarely burns, gradually tans or tans with ease), Type V and VI (dark brown, black, very rarely or never burns, tans very easily). We will therefore pre-specify three groups for analysis (type I/II, type III/IV, and type V/VI). It is possible that home vs. office based phototherapy will be associated with differences in tolerability (i.e., burns) in those with very fair skin type (i.e., type I/II) due to increased penetration of ultraviolet rays, and may be associated with differences in effectiveness in darker skin types (type V/VI) due to decreased penetration of ultraviolet rays. An example of the dosing regimen can be found in the Appendix A.

2 Study Objectives

2.1 Primary Objective

To compare the effectiveness, safety (tolerability), and duration of treatment response at 12 weeks of home versus office-based NB-ultraviolet B phototherapy for the treatment of psoriasis

2.2 Secondary Objectives

To assess the impact of phototherapy delivered at home or in the office on:

- Body surface area (BSA) affected by psoriasis multiplied by the PGA (BSAxPGA)
- Phototherapy number and dose

- Concomitant topical psoriasis treatment
- Concomitant oral or biologic psoriasis treatment
- Patient reported time spent on phototherapy
- Patient reported time and cost associated with travel
- Duration of treatment response during observation period

3 Investigational Plan

3.1 General Design

The design is a large pragmatic randomized active comparator study of home vs. office based NB-UVB phototherapy for the treatment of psoriasis. Both comparator treatments are considered standard of care and thus this would be classified as a Phase IV study. Dosing of phototherapy will be based on a standardized protocol (see APPENDIX A) or a standard protocol that is routinely used by the local investigators in order to reflect routine clinical practice. The study will include up to 1050 patients stratified by Fitzpatrick skin type (350 skin type I/II, 350 skin type III/IV, we anticipate that approximately 80 participants will be enrolled in Skin type V/VI). We hypothesize that home phototherapy will be noninferior to office based phototherapy. There will be a recommended screening period of up to 28 days, to allow for obtaining informed consent and administrative procedures necessary for office based or home phototherapy, as well as randomization. Patients will be randomized (1:1) to home vs. office-based phototherapy within 28 days of the baseline visit or per standard of care of individual practices. If the patient is randomized to home phototherapy a machine will be delivered to their home and phototherapy treatment initiated within 14 days of randomization. If the patient is randomized to office phototherapy, the first treatment should occur within 14 days of randomization. The patient will be assessed by the dermatologist (or PA or NP or other gualified clinician as appropriate to the clinical practice) at baseline and at 12 (plus or minus 2) weeks after start of phototherapy, or at the time of discontinuation of phototherapy, whichever comes first. Patients will receive phototherapy treatments about 3 times per week for 12 weeks. They will then be observed for an additional 12 weeks. With each phototherapy treatment, patient response to prior phototherapy treatment will be collected by clinic staff or recorded on the phototherapy machine via patient assessment. Patients will complete a survey every 4 weeks for the duration of the study that captures patient reported outcomes.

3.1.1 Screening Phase

Patients will be recruited from the sites' clinical practice. Patients being considered for phototherapy will be offered the opportunity to participate in this study at the discretion of the clinician. Electronic consent will be obtained before any study specific procedures are conducted. Electronic assent will be obtained from children eligible to participate and written consent will be obtained by their parent or authorized legal guardian. Consent and assent can be obtained remotely or in person.

The screening phase begins at the time of obtaining informed consent and continues until the patient is randomized (up to a total of 28 days or longer based on the local practice standard of care). The length of time between screening and randomization will be allowed to vary based on local practice standard of care as this is a pragmatic trial and thus we aim to reflect usual clinical practice. In usual practice, clinicians vary on the duration of time between when they evaluate a patient and when the patient actually starts phototherapy. This period can be delayed due to administrative issues (i.e., obtaining insurance approvals, etc), availability of phototherapy appointments, and patient schedule issues. The baseline visit will occur during the screening phase. Information collected at the baseline visit will be collected again if the patient sees the local provider again for routine care prior to randomization. The site will confirm that the patient is eligible for randomization by having obtained any insurance approvals necessary for office based treatment and confirming with the patient that they are willing to be randomized to office based phototherapy based on any additional information obtained from the insurance approval process (such as required co-pays or other cost sharing agreement). Patients are then randomized, and should receive their first treatment within 14 days of randomization.

3.1.2 Study Intervention Phase

Patients should receive a first treatment with phototherapy according to the group they are assigned via randomization within 14 days of randomization. Patients who do not start phototherapy within 14 days of randomization will be assigned a start date at day 14 post randomization which will define their start and end of the intervention phase. Patients will be treated with home or office based phototherapy approximately 3 times per week for up to 12 weeks. The intervention stage will start on the date of the first treatment (or 14 days after randomization, whichever comes first) and continue for 84 days. Patients will be evaluated by the clinician prior to start of phototherapy (during the baseline visit) and at the conclusion of phototherapy treatment or by day 84 (plus or minus 14 days), whichever comes first.

3.1.3 Observation Phase

The observation phase will start 84 days after the first treatment is received (or 14 days after randomization, whichever comes first) by the patient and will continue for an additional 84 days.

3.1.4 Allocation to Interventional Group

Randomization will be implemented using randomly permuted blocks of size two or four, stratified on clinic and skin type. This will maximize blinding of investigators to the randomization schema and achieve balanced groups within study sites and skin types. A randomization table will be created by the senior biostatistician at the University of Pennsylvania and built into the study application ("app") by the Clinical Research Computing Unit (CRCU). The app will be loaded on iPads used to collect data by the study sites. When a new patient is enrolled in the study, the app will generate a new patient id and provide a treatment assignment. The master list of patient ids and treatment assignments will be stored electronically at the CRCU. Data analysts will be blinded as to group assignment by using codes for randomization groups.

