4.2 Exclusion Criteria

Exclusion criteria:

- 1. Patients who are judged unable or unwilling to comply with either in office or in home phototherapy due to time, work, school, or other financial constraints
- 2. Patients judged unable to follow home phototherapy protocol due to failure to demonstrate understanding of the following:
 - a. How to operate the phototherapy device
 - b. How to follow the dosing protocol
 - c. Requirement to wear protective eyewear and genital protection equipment
- 3. Patients with known history of lack of efficacy to phototherapy or treated with phototherapy 14 days prior to baseline visit.
- 4. Psoriasis predominantly located on scalp, body folds, genitals, palms and/or soles or with a physician global assessment average of ≤ 1.0
- 5. Patients deemed unsafe to be treated with phototherapy:
 - a. History of photosensitivity or autoimmune disease such as lupus or dermatomyositis which can be aggravated by ultraviolet radiation
 - b. History of arsenic intake
 - c. Unable to tolerate standing for required duration of treatment due to age or physical function
 - d. History of melanoma or multiple non-melanoma skin cancers that in the opinion of the principal investigator contraindicates treatment with phototherapy
- 6. Clinical site deems the participant is ineligible for reason other than eligibility or screening criteria.

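### Permuted blocks of two or four within clinic and skin type do not maximize blinding to the schema: if both sizes are equally likely, a site that tracks its assignments can know about one in ten in advance, and a larger maximum block size would cut this to about 2.4%

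*Combined protocol and SAP*

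**What the plan says.** Section 3.1.4 (Allocation to Interventional Group) sets the scheme: "Randomization will be implemented using randomly permuted blocks of size two or four, stratified on clinic and skin type". Section 3.1 gives the ratio: "Patients will be randomized (1:1) to home vs. office-based phototherapy". The reason offered in 3.1.4 is: "This will maximize blinding of investigators to the randomization schema and achieve balanced groups within study sites and skin types". Assignments are released by software: "When a new patient is enrolled in the study, the app will generate a new patient id and provide a treatment assignment". The master list is held centrally. The only masking described is of analysts: "Data analysts will be blinded as to group assignment by using codes for randomization groups".

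Three other passages bear on whether a predicted assignment could be used:
- Under 3.1.1 (Screening Phase), patients are "offered the opportunity to participate in this study at the discretion of the clinician", and the time from screening to randomization may vary with local practice.
- Exclusion 6 in section 4.2 reads: "Clinical site deems the participant is ineligible for reason other than eligibility or screening criteria".
- The primary model in section 8.1 contains treatment arm and skin type only.

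**The concern.** The documents do not call the trial open-label, but home and office treatment cannot be masked at the clinic. Under section 6.1 the site either prescribes the home unit or books the office sessions. Staff therefore hold the full assignment history of each of their strata, and the protocol tells them the block sizes. From these they can sometimes deduce the next assignment.

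A deduced assignment matters only if it can be acted on. Sites keep some control over whom they approach, when a consented patient is randomized, and whether exclusion 6 is used. A preference between arms is conceivable: the home unit is free to the patient (section 12.2), whereas office treatment may carry co-payments (section 3.1.1). If patients with a better outlook were steered to one arm, the difference would pass into both co-primary outcomes, because the model adjusts for neither clinic nor baseline severity. Steering towards home would favour a conclusion of non-inferiority.

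**Working it through.** **The plan's own figure.** The documents give no predictability figure. The nearest is the sample size in section 8.3. With 50% response in both arms, a 15-point margin and one-sided 2.5%, n = 2 × 0.25 × (1.960 + 0.842)² / 0.15² = 174.4, so 175 per arm, as stated. Power is 80.1% at 175 per arm and 99.8% at 525 per arm (stated: 99%). These are used below only to price imbalance.

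**Stratum size.** Section 4.3 gives about 20 to 40 sites. Section 3.1 gives 350 patients in each of types I/II and III/IV and about 80 in V/VI.
- I/II and III/IV: 350/40 = 8.75 to 350/20 = 17.5, so about 9 to 17 per clinic. I use 13 as the central case.
- V/VI: 80/40 = 2 to 80/20 = 4 per clinic.

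The Study Summary instead gives 350 for V/VI, which would put that stratum in the 9 to 17 range as well.

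**When an assignment is certain.** In a 1:1 block of two or four, the running difference between arms returns to zero at the end of each block. It reaches two only when a block of four opens with two like assignments, and the next two are then fixed. At any other point a block of two may explain the history or may come next, so nothing is certain.

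**Certain share.** Let p be the share of blocks that are of size two. A block of four opens with two like assignments with probability 1/3, and then two assignments are certain. In the long run:

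share = (1 − p) × (1/3) × 2 / [2p + 4(1 − p)]

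- p = 0.50: 0.333/3.0 = 11.1%
- p = 0.75: 0.167/2.5 = 6.7%
- p = 0.25: 0.500/3.5 = 14.3%

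Exact enumeration at finite length, for an observer who knows the possible sizes and all earlier assignments in the stratum, gives slightly less:

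| Patients in stratum | p = 0.75 | p = 0.50 | p = 0.25 |
|---|---|---|---|
| 9 | 5.5% | 9.5% | 12.5% |
| 13 | 5.8% | 10.0% | 13.1% |
| 17 | 6.0% | 10.2% | 13.3% |

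In V/VI the share is 0 at two patients and (1 − p)/6 at four, which is 8.3% at p = 0.5.

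**Guessability.** The best guess is always the arm that is behind. For the second patient in a stratum it is right with probability (1 + 2/3)/2 = 83%. Blocks of 4, 6 and 8 would give (2/3 + 3/5 + 4/7)/3 = 61%. Averaged over 13 patients:

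| Sizes, equally likely | Certain | Best guess correct |
|---|---|---|
| 2/4 | 10.0% | 70.4% |
| 2/4/6 | 3.4% | 68.4% |
| 4/6 | 6.0% | 67.3% |
| 4/6/8 | 2.4% | 66.0% |

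Every alternative does better than 2/4 on both measures.

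**Cost in balance.** This was simulated with 30 clinics of uneven size (gamma weights, assumed), comparing 4/6/8 with 2/4.
- One skin type of 350: mean absolute imbalance 4.7 against 3.7; 95th percentile 12 against 10. Power at the 95th percentile is Φ(0.15/√(0.25/181 + 0.25/169) − 1.96) = 80.08%, against 80.10% for 180 and 170.
- All 1050: mean 7.6 against 6.4; power 99.81% in both cases.
- V/VI, 80 patients: mean 4.4 against 3.6. The efficiency of a clinic-stratified comparison falls from about 0.87 to 0.81.

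Results for the 350 and 1050 comparisons are similar with 20 and 40 clinics.

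**The case against.** The strongest case for the plan has four parts.

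**The scheme has real safeguards.** Release by the app and a central list prevent anyone reading ahead. Varying the block size also helps: over 12 patients, fixed blocks of four would make 33% of assignments certain and fixed blocks of two 50%. This stands, but it does not stop deduction from past assignments.

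**Steering is constrained.** Patients must be willing and able to use either arm. Consent, insurance approval and confirmed willingness come before randomization. With a screening interval of weeks, the assignment pending when a patient is approached may go to someone else. This reduces the scope for steering but leaves control over timing and over exclusion 6.

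**The gain in guessability is modest.** Excess over chance falls from 20.4 to 16.0 points, so nearly four-fifths remains. This stands. It reflects small strata at sites that know the arm. The clear gain is in the certain share.

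**No bias in the result is shown.** This also stands. The documents give nothing from which to express the exposure in response-rate points against the 15-point margin.

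A reader might infer that blocks of two are the culprit. The arithmetic does not support that: more blocks of two lower the certain share, and 2/4/6 has fewer certain assignments than 4/6. Blocks of two mainly raise guessability. A reader might also count the unmasked PGA rating as part of this problem. It is a separate question of outcome assessment, and no block size changes it.

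**Conclusion.** The claim that the scheme maximizes blinding is not correct, since other permuted-block schemes with the same stratification are less predictable on both measures. In skin types I/II and III/IV about 10% of assignments are certain in advance and about 70% can be guessed. In V/VI, 0 to 8% are certain.

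These figures rest on two assumptions that the documents do not settle: that the two sizes are equally likely, and that someone at the clinic tracks assignments within skin type. One in ten is therefore not a fixed property of the plan. The range is 5.5% to 13.3% over the mixes examined, and the predictions have no practical effect where nobody keeps track.

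A reader might conclude that concealment has failed or that the comparison is biased. The documents do not support that. They show an avoidable exposure to selection bias that the primary model would not correct. Sample size and power are unaffected. The change is worth making because it costs little.

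**What to change.** 1. For all future randomization lists, raise the maximum block size and vary the sizes at random, for example 4, 6 and 8.
2. Move the block sizes to a restricted document and remove them from the site-facing protocol. Tell sites only that sizes vary.
3. In section 3.1.4, delete the statement about maximizing blinding to the schema. The statement about balance can stay.

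The cost is a new randomization table for blocks not yet started and a short text amendment. Imbalance rises by about one patient on average in a skin type of 350, with a power loss below 0.1 percentage point. The main downside is in V/VI, where clinics hold only 2 to 4 patients and within-clinic balance worsens. Section 8.1 says non-inferiority cannot be tested in that group, and the primary model does not adjust for clinic, so this is tolerable.
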